# 4.3 WITHDRAWL/TERMINATION CRITERIA

Patients who do not undergo the placement of a ureteral stent following a routine urological procedure will be withdrawn from the study. If the patient was scheduled to undergo the stent placement and for any reason the plan changed or was cancelled that patient will be taken off the protocol and considered discontinued. The patient spot will be replaced and the study ID number will not be reused. This will allow the protocol to be completed once 94 patients have completed treatment based on statistical calculations from the Biostatistics department (below).

Patients will be allowed to withdraw from the study at any time. If a patient cancels permission to use their health information the research team will stop collecting any additional information about them moving forward. The research team may use and share information that was gathered before they received the patient's withdrawal. The entire study may be discontinued for any reasons without the patients consent by the investigator conducting the study.

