# **5.3 STUDY PROCEDURES**

To assess ureteral stent symptoms, we will be conducting the Ureteric Stent Symptoms Questionnaire (USSQ). The USSQ was created by Joshi et al as an instrument to measure stentrelated morbidity. The USSQ has been validated as a reliable instrument to measure the impact of ureteral stents. This validated questionnaire has been used in many previous studies regarding stent pain. In our study, the USSQ will be conducted prior to stent placement, on POD1, POD7 (or just prior to the time of stent removal if the removal occurs prior to day 7), and POD30. Basic demographic information, stent duration, stent size, stone location/size and obstructing vs. non-obstructing (if applicable), post stent insertion complications, drug diary information and questionnaire responses will be entered into a REDCap database for storage and analysis. The stent diameter will be 6Fr for all patients in the study. The appropriate stent length will be assigned to the patient based on cross sectional imaging. If cross sectional imaging is not available then stent length with be measured using a open-ended catheter to measure ureteral length. A small portion of these patients will be seen in the emergency department or while they are having an acute pain episode, so we expect that some of the pre-stenting questionnaires may not provide an accurate baseline for symptoms in these patients, hence the POD30 questionnaire will be obtained.

After informed consent is obtained, the patient will be prospectively randomized to either treatment arm in an open-label fashion using REDCap's randomization function to determine which therapy they will receive after stent placement. In the event that a patient does not find relief with their particular treatment arm, they will be permitted to receive additional narcotics or Pyridium. Should the patient continue to have unrelieved symptoms, treatment crossover is allowed since the study is designed in an intent-to-treat fashion.

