# 5.4 STUDY DESIGN AND SAMPLE SIZE

Total sample size: 100

The study will be conducted as a randomized comparative effectiveness trial with two arms. Subjects will be randomized to one of two treatments WITH either hyoscyamine or tamsulosin. Our hypothesis is that the hyoscyamine is at least as effective as tamsulosin in treating lower urinary tract symptoms. Symptoms will be quantified using the Urinary Symptom Index (USI) of the validated Ureteral Stent Symptom Questionnaire (USSQ). To address the hypothesis, the study will be conducted as a non-inferiority trial, following the hypothesis that hyoscyamine is not inferior to tamsulosin by more than a 15% margin in terms of the USI. The sample size was estimated using the PowerTOST package for the R statistical environment, based on a nominal power of 80% and an alpha-level of .025 for the one-sided t-test. Our null hypothesis is therefore that the mean USI for those treated with tamsulosin is more than 15% greater than those treated with hyoscyamine, so that by rejecting it, we may conclude hyoscyamine is not-inferior to tamsulosin by more than a 15% margin of USI for treating lower urinary tract symptoms. Furthermore, we assume that the coefficient of variation (CV) for the mean Urinary Index Score

will be similar to that in Park, et al.20 The CV in that study for the Urinary Symptom Index at week 2 after stent placement for the tamsulosin group was approximately .25. This is slightly higher, but similar to the CV of .22 for the USI in Maldonado-Avila, et al. which collected data at week 1, and therefore should be slightly conservative.21 Using these assumptions, we estimated that the sample size for each arm would need to be approximately 47, in order to have the desired power.

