# **5.5 DATA ANALYSIS**

The main hypothesis of the non-inferiority of hyoscyamine to tamsulosin for treating lower urinary tract symptoms will be tested using a t-test for non-inferiority of the change in USI between POD1 and POD7 (or day of stent removal if removed before day 7) in each treatment arm. This should be slightly more powerful than the t-test at POD7 alone that we used to estimate the sample size, but there are not enough data available for the distribution at POD1 in order to make a good estimate of the change. The non-inferiority margin will be 15% of the change in USI. The primary analysis will be conducted as intention-to-treat (ITT). That is, subjects will be analyzed as belonging to the arm they were randomized to, irrespective of later crossover or other modifications. This approach is in line with the current statement on Consolidated Standards of Reporting Trials (CONSORT). Descriptive statistics will be used to describe the results from all USSQ domains at each timepoint (i.e. mean and standard deviation, along with confidence intervals for urinary symptom index, pain symptom index, etc.). We will also conduct non-inferiority tests of change in score for ITT with hyoscyamine versus tamsulosin for the other domains spanned by the USSQ, including pain symptom index, general health index, work performance index, and sexual matters between POD1 and POD7, although we may not be wellpowered to detect non-inferiority for these additional domains.

The secondary goal of determining if there are differences in the amount of additional medications need to treat stent-related discomfort between treatment arms will be examined primarily through descriptive statistics. The drug diaries of all subjects will be used to tabulate the kinds and amounts of additional medications used. For each subject, the number of days that additional medications were used will be counted. The proportion of days that additional medications were used will be calculated for each group and 95% confidence intervals will be calculated.

Finally, we will also calculate the informed consent rate, and the discontinuation rate for those patients needing to be removed from the study in each arm.

In all cases, a p-value  $\leq$  .05 will be taken as a statistically significant result.

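### The 80% power belongs to a test of the POD7 USI level, not to the planned primary test of change, whose margin (15% of the change) has no value at planning

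*Combined protocol and SAP*

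**What the plan says.** Section 5.4 (Study Design and Sample Size) states the hypothesis that "hyoscyamine is not inferior to tamsulosin by more than a 15% margin in terms of the USI". The calculation is "based on a nominal power of 80% and an alpha-level of .025 for the one-sided t-test" and takes its CV of about .25 from the tamsulosin group of a cited trial at week 2. A second cited trial, with a CV of .22 at week 1, is offered as support. The result is "we estimated that the sample size for each arm would need to be approximately 47". Section 4.3 carries this forward: the protocol is complete "once 94 patients have completed treatment based on statistical calculations".

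Section 5.5 (Data Analysis) makes the primary analysis a non-inferiority t-test on the change in USI from POD1 to POD7, or to the day of stent removal if earlier. Three statements there matter:

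- On power: "This should be slightly more powerful than the t-test at POD7 alone that we used to estimate the sample size".
- On planning data: "there are not enough data available for the distribution at POD1 in order to make a good estimate of the change".
- On the margin: "The non-inferiority margin will be 15% of the change in USI".

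Neither section gives a mean change, an SD of the change, a POD1-POD7 correlation, or a margin in USI points.

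**The concern.** Two things change between sizing and testing: the endpoint (level to change) and the base of the margin (15% of the level to 15% of the change). Section 5.5 acknowledges the first but does not mention what the second does to power. A change is usually smaller than the level it is measured from, so 15% of it is a smaller margin, while its SD need not shrink in proportion.

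The margin is also incompletely defined. The text does not say which arm's change it refers to, or whether that is the observed or the expected change. If mean USI does not improve from POD1 to POD7, the rule gives a margin of zero or less.

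Two consequences follow. The trial may have little chance of showing non-inferiority even if the drugs are equally effective. And because the threshold is not fixed beforehand, in an open-label trial, the primary conclusion could depend on choices made after the data are seen.

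**Working it through.** **Inputs from the documents.** One-sided alpha .025, power 80%, level margin 15%, CV .25, about 47 per arm (Section 5.4); change endpoint with margin 15% of the change (Section 5.5).

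**Assumed, because the documents give no values.** True difference 0; POD7 mean scaled to 1; f = mean improvement from POD1 to POD7 as a share of the POD7 mean; r = POD1-POD7 correlation.

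**Formula.** Two-sample noncentral t, n per arm, df = 2n − 2, noncentrality = margin / (SD × √(2/n)). At n = 47, df = 92 and the critical value is 1.986.

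**1. The plan's own figure.** Margin .15, SD .25, n = 47: noncentrality = .15 / (.25 × √(2/47)) = 2.909, power 82.1%. The smallest n for 80% is 45 (80.4%). That is within two of the stated figure, so the sizing matches a margin of 15% of the level.

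**2. The planned test, with no assumption about correlation.** With the margin treated as a known constant, noncentrality = .15 × mean(change) / (SD(change) × √(2/47)). Power of 80% needs a noncentrality of 2.831, so SD(change)/mean(change) must be at most .15 / (2.831 × √(2/47)) = 0.257. A ratio of 0.5 gives 30.1% power and a ratio of 1.0 gives 10.7%.

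**3. The planned test over a range of assumptions.** The margin is .15 × f.

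- Constant SD: SD .25 at both visits, so SD(change) = .25 × √(2(1 − r)).
- Constant CV: CV .25 at both visits, so the POD1 SD is .25 × (1 + f) and SD(change) = √(SD1² + .25² − 2 × r × SD1 × .25).

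Power at 47 per arm:

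| Case | f | r = .5 | r = .8 | r = .9 |
|---|---|---|---|---|
| Constant SD | .2 | 8.3% | 14.7% | 25.1% |
| Constant SD | .5 | 30.1% | 62.4% | 89.6% |
| Constant CV | .2 | 7.5% | 12.3% | 19.2% |
| Constant CV | .5 | 19.2% | 34.5% | 49.2% |
| Constant CV | 1.0 | 38.3% | 57.4% | 68.2% |

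Example (constant SD, f = .5, r = .5): margin .075, SD .25, noncentrality .075 / (.25 × √(2/47)) = 1.454, power 30.1%.

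Patients per arm for 80% power, r = .5 and r = .8:

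- Constant SD: 1,092 and 438 at f = .2; 176 and 71 at f = .5.
- Constant CV: 1,353 and 568 at f = .2; 307 and 150 at f = .5.

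Under constant SD, keeping 80% at 47 per arm needs f of about .97 (r = .5), .62 (r = .8) or .44 (r = .9).

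**4. The claim of slightly greater power.** Keep the absolute margin at .15 on the change scale, with equal SDs. Power is 68.2% at r = .3, 74.8% at r = .4, 82.1% at r = .5 and 89.6% at r = .6. The claim is therefore true only for r above .5 and with the level margin retained. Section 5.5 does not retain it.

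**The case against.** The strongest reply is that the plan is open about part of this. It says the sizing used POD7 alone and that POD1 data were lacking, and sizing on a related endpoint is a legitimate choice when data are scarce. The Section 5.4 calculation is also sound in itself: 47 per arm is exactly what the t-test needs for a CV of about .2545 to .2568. Both observations are fair. The fault is that sizing and test do not match, and the change in the base of the margin is not disclosed.

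The 0.257 limit depends on treating the margin as a known constant. If it is read instead as 15% of the tamsulosin arm's true change, the contrast is hyoscyamine change − 0.85 × tamsulosin change. The variance factor is then 1 + .85² = 1.7225 instead of 2, and the limit becomes about 0.277. With constant SD and f = .5, power is 34% at r = .5 and 69% at r = .8. That is a modest gain which does not rescue the plan.

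Low power is not proven. A large change with high correlation would reach the target (about 90% at f = .5, r = .9, constant SD), and nothing in the documents favours f = .2 over f = .5 or more. This limits the claim to power being unsupported.

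Finally, the 82% for a POD7 test holds for a raw-scale test with CV .25. At a CV of .2545 to .2568 the power is 80.0% to 80.7%. On a log scale with a ratio margin of 1.15, 47 per arm gives 77.7% and 50 are needed. Section 5.4 does not state the scale.

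**Conclusion.** The concern holds and must be fixed. The stated 80% power is not a property of the primary test, and the primary margin has no value in USI points at planning. Under the assumptions shown, power at 47 per arm runs from about 8% (a change of one fifth of the POD7 mean, r = .5) to about 90% (a change of one half, r = .9, constant SD). With constant CV it stays below 80% even when the change equals the POD7 mean, for r up to .9. These figures rest on assumed values of f and r and a true difference of 0; they show how wide the uncertainty is and do not estimate the trial's actual power. The lack of a usable margin depends on none of them: the rule names no arm, does not say whether the change is observed or expected, and fails if mean USI does not improve.

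**What to change.** Use one endpoint and one margin in Sections 5.4 and 5.5.

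**Preferred.**

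- Make USI at POD7 (or at stent removal if earlier) the primary endpoint, tested with the unadjusted t-test used for sizing.
- State the margin beforehand as a fixed number of USI points, equal to 15% of the tamsulosin-group mean in the cited study that supplied the CV of .25. That mean is not in the documents and has to be taken from the study.
- Reword the null hypothesis in Section 5.4 to the same reference; it now expresses the 15% relative to the hyoscyamine mean. State the scale of the sample size calculation.
- Delete the sentences "The non-inferiority margin will be 15% of the change in USI" and "This should be slightly more powerful than the t-test at POD7 alone that we used to estimate the sample size".
- If an adjusted analysis is added, adjust for the pre-stent USI. POD1 follows stent placement and may already reflect treatment. Section 5.3 warns that "some of the pre-stenting questionnaires may not provide an accurate baseline for symptoms in these patients"; this would reduce the gain in precision but would not bias a randomized comparison.

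**Alternative.** Keep the change endpoint, state a fixed margin in points, and restate power and sample size with explicit assumptions for the SD of the change and the correlation.

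**Cost.** The preferred route changes wording only: the POD7 questionnaire is already scheduled, and the 94 completers give about 82% power at CV .25 (raw scale), with less slack if the CV is slightly higher. The alternative may need more patients, depending on the assumptions made.

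### Four further USSQ domains are to be tested for non-inferiority without a margin, a test order or a stated one-sided level; report them as estimates and reserve the claim for the USI

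*Combined protocol and SAP*

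**What the plan says.** Section 5.5 (Data Analysis) makes the USI the main hypothesis and then adds: "We will also conduct non-inferiority tests of change in score for ITT with hyoscyamine versus tamsulosin for the other domains". The domains are listed as "including pain symptom index, general health index, work performance index, and sexual matters between POD1 and POD7". The same sentence admits that power for them may be inadequate, but gives no figure.

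The margin in 5.5 reads "The non-inferiority margin will be 15% of the change in USI". Section 5.4 (Study Design and Sample Size) also ties its margin to the USI: "hyoscyamine is not inferior to tamsulosin by more than a 15% margin in terms of the USI". No margin appears for any other domain.

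Section 5.5 closes with a rule for every analysis: a p-value of .05 or less "will be taken as a statistically significant result". It does not say whether the p-value is one- or two-sided. Section 5.4 does, for the sample size: "based on a nominal power of 80% and an alpha-level of .025 for the one-sided t-test".

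**The concern.** A non-inferiority test is defined by its margin. With none stated for pain, general health, work performance or sexual matters, each of these tests lacks a null hypothesis and cannot be run as written. Someone would have to choose the margin later, in an open-label trial and possibly with the data in view.

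The obvious stopgap is to apply the USI rule of 15% of the change to each domain. That works badly. A domain that moves little between POD1 and POD7 gets a margin close to zero, and a domain that does not improve gets no usable margin at all.

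Two further problems are distinct and should be kept apart. The first is multiplicity: four extra tests, each allowed to count as significant on its own, with no order and no adjustment. The second is information: if power is low, a failed domain test says little and could be misread as evidence of inferiority. Low power does not raise the false-positive rate of a single test. Pain is likely to be the domain readers most want to quote, so the status of its result should be settled in advance.

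**Working it through.** **Inputs from the documents.** Four extra domains (5.5). One-sided alpha .025 and power 80% (5.4). Margin 15% (5.4). CV "for the tamsulosin group was approximately .25" (5.4, USI only). For size, "we estimated that the sample size for each arm would need to be approximately 47" (5.4). The documents give no mean change and no SD of change for the four domains. For the USI too, 5.5 says the data are insufficient to estimate the change.

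**Step 1. The plan's own sample size.** Two-arm non-inferiority t-test, true difference 0, margin 0.15, SD 0.25, so the standardised margin is 0.15/0.25 = 0.6. With n per arm, the noncentrality is 0.6 × √(n/2) on 2n − 2 degrees of freedom.
- n = 45: noncentrality 2.85, power 80.4%. This is the smallest n that reaches 80%.
- n = 47: noncentrality 2.91, power 82.1%.

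On the log scale with margin ln(1.15) the answer is 50 per arm. The stated 47 lies between these two results, so it is accepted as the size for the steps below.

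**Step 2. Multiplicity across the four domains.** Worst case: hyoscyamine is inferior by exactly the margin in all four domains at once. The chance of at least one false non-inferiority finding is 1 − (1 − α)^4 if the tests are independent. Domains of one questionnaire are probably positively correlated, so a multivariate normal simulation (500,000 draws, common correlation .5) is shown beside it.

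| Level per test | Independent | Correlation .5 |
|---|---|---|
| One-sided .025 | 1 − .975^4 = 9.6% | about 7.7% |
| One-sided .05 | 1 − .95^4 = 18.5% | about 14.3% |

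The first row applies if the .05 in 5.5 is two-sided, which agrees with 5.4. The second applies if it is one-sided. The text of 5.5 allows either.

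**Step 3. Power under a carried-over margin (assumption).** Suppose each domain takes a fixed margin of 15% of its mean change, and that mean change is k SDs of the change score. The standardised margin is 0.15k and, at 47 per arm, the noncentrality is 0.15k × √23.5 = 0.727k on 92 degrees of freedom. The one-sided .025 critical value is 1.986. The arms are taken as truly equal.

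| Mean change k (assumed) | Margin in SD | Power, one-sided .025 | Power, one-sided .05 | Ratio to the 2.5% pass rate at the margin |
|---|---|---|---|---|
| 0.5 | 0.075 | 5.5% | 10.0% | 5.5/2.5 = 2.2 |
| 1 | 0.15 | 10.7% | 17.8% | 10.7/2.5 = 4.3 |
| 2 | 0.30 | 30.1% | 42.0% | 30.1/2.5 = 12 |
| 4 | 0.60 | 82.1% | 89.3% | 82.1/2.5 = 33 |

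**Step 4. Power under a level-based margin (alternative assumption).** If the margin were 15% of the score level, as 5.4 words it for the USI, power at 47 per arm and one-sided .025 would be 82% at a CV of 0.25, 30% at 0.5 and 11% at 1.0. The CVs for the four domains are not given.

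**The case against.** The plan is not silent on priority. Section 5.4 frames hypothesis, null and margin in USI terms, section 5.5 treats the other domains as additional, and the secondary objectives in 3.2 do not list them. The low-power caveat sits in the same sentence as the tests. A reader can fairly see an implied order of primary and supportive results. That stands, but it is not a gatekeeping rule. The caveat prepares the reader for failed tests; it supplies no margin and does not restrain a claim from a passed one.

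The error rates are a ceiling. A reader might infer that 18.5% is the error rate to expect. The documents do not support that: it needs one-sided .05, independence, and inferiority by exactly the margin in all four domains. The only sidedness in the documents is one-sided .025, which gives 9.6% or less.

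A reader might also infer from the low power that these tests hardly distinguish an equal drug from an inferior one. The documents do not support that either. Even under the carried-over margin, an equal drug passes 2.2 to 12 times as often as one at the margin for changes of 0.5 to 2 SD, and a level-based margin with a CV near 0.25 would give high power. A tight margin also makes non-inferiority harder to claim, so a shrinking margin is a problem of definition and not a route to easy claims.

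Finally, removing the tests is not the only remedy. Justified domain margins with ordered testing would also work.

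**Conclusion.** The point holds as a gap in definition with a modest error-control consequence. It does not touch the primary USI test. The firm part rests on the text alone: four non-inferiority tests, no margin for any of them, no order or adjustment, and a p ≤ .05 rule whose sidedness is not reconciled with 5.4.

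The size of the multiplicity problem is at most 9.6% at one-sided .025 each and at most 18.5% at one-sided .05 each, taking the domains as independent or positively correlated; at correlation .5 the figures are about 7.7% and 14.3%. All are worst cases.

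The power range of about 5.5% to 30% is conditional on a carried-over margin, 47 per arm, true equality and assumed changes of 0.5 to 2 SD. It illustrates how uninformative the tests could be; it is not a finding about these domains.

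**What to change.** In section 5.5, replace the sentence on non-inferiority tests for the other domains with wording such as: *For the other USSQ domains, the between-arm difference in change from POD1 to POD7 (or stent removal, if earlier) will be reported with its two-sided 95% confidence interval. No non-inferiority test or verdict will be made for these domains. Only the USI test supports a non-inferiority claim.*

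Limit the closing p-value sentence so that the USI non-inferiority test uses one-sided .025, in line with 5.4.

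The cost is wording only. Section 5.5 already plans means, SDs and confidence intervals for all domains by time point; the addition is the interval for the between-arm difference. What is lost is the option of non-inferiority statements on domains the plan already says may be underpowered. If the sponsor wants to keep such statements, each domain needs its own fixed margin with a stated source, and the domains should be tested in a fixed order after the USI, each step at one-sided .025, which holds the family error rate at .025.

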# **1.0 STUDY SUMMARY**

# **1.1 AIM AND HYPOTHESIS**

The objective of this project is to compare the efficacy of hyoscyamine to tamsulosin monotherapy in treating lower urinary tract symptoms in patients with indwelling double-J ureteral stents.

Ureteral stents are routinely used in a variety of urologic conditions. Unfortunately, indwelling ureteral stents commonly cause significant pain and discomfort due to irritation to the urinary system. Many studies have looked at methods to reduce these uncomfortable symptoms ranging from altering stent designs to pharmacologic therapies attempting to alleviate stent-discomfort. However, stent-related discomfort continues to be an issue and is often the cause of their removal earlier than planned. While the efficacy of certain alpha blockers and anticholinergics in treating stent-related symptoms have been studied, the data for the use of hyoscyamine in this setting is lacking. A literature search yielded no studies evaluating the use of hyoscyamine in this setting to date. We hypothesize that hyoscyamine (brand name Levsin) is equivalent to tamsulosin in treating lower urinary tract symptoms in patients with indwelling double-J ureteral stents due to its anticholinergic properties. Furthermore, we hypothesize that patients in the hyoscyamine arm will not require additional pain medications (e.g. Pyridium, narcotics) to help control stent-related discomfort compared to the tamsulosin arm.

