# **3.2 SECONDARY OBJECTIVE**

To determine if there is a difference between the amount of additional medications needed to treat stent related discomfort between patients receiving hyoscyamine versus those that receive tamsulosin.

To determine factors contributing to patients needing additional medication for treatment of stent-related discomfort.

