The first arm is hyoscyamine 0.125 mg tab sublingual every 4 hours as needed for discomfort, and the second arm is tamsulosin 0.4mg tab orally daily. Both dosing regimens are standard prescription orders. Both medications are routinely used in our practice, so patients are not being exposed to new safety risks compared to non-study patients. Risks are reasonable, as the medications used in this study are already commonly used in our daily practice. Patients will be given contact numbers for the Urology Department should they have any adverse side effects or concerns. Hyoscyamine is an anticholinergic and can cause side effects including constipation, dry mouth, drowsiness, headache, or lightheadedness. Tamsulosin is an alpha blocker and can

cause side effects including dizziness, fatigue, nasal congestion, syncope and retrograde ejaculation. Patients who have taken alpha blockers are at risk for intraoperative floppy iris syndrome if they are going a cataracts surgery in the near future. Patients will be advised to immediately stop the medicine and seek medical care if they develop the rare but severe reactions of skin rash, swelling, confusion, irregular or fast heartbeat, eye pain, or hallucinations. As part of the standard treatment pathway for post-stent insertion, patients are also sent home with a narcotic pain medication to help with pain and discomfort. Our pathway is to prescribe all patients with 10 tabs of Norco 5/325 1-2 tabs po q6H PRN unless there are contraindications or allergies to this specific narcotic, in which case they are prescribed an alternative narcotic with Percocet 5/325 1-2 tabs po q6H PRN. Patients will be given a drug diary to document their usage of the study medications for stent discomfort, including their narcotic usage, so that this information can be tracked as well. Patients will stop drug diary at time of stent removal.

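### The secondary question is about the amount of additional medication; section 5.5 tabulates amounts, but its only per-subject measure and only medication-use interval are on days with any use

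*Combined protocol and SAP*

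**What the plan says.** The secondary objective in section 3.2 asks whether there is a "difference between the amount of additional medications needed to treat stent related discomfort" between the hyoscyamine and tamsulosin arms. Section 5.5 repeats the question and sets the level of analysis: "differences in the amount of additional medications need to treat stent-related discomfort between treatment arms will be examined primarily through descriptive statistics".

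Section 5.5 then plans three things from the drug diaries:

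- All diaries will be used to "tabulate the kinds and amounts of additional medications used". No unit is given, and the text does not say whether the table is per patient or pooled.
- A per-patient count: "For each subject, the number of days that additional medications were used will be counted".
- A group summary: "The proportion of days that additional medications were used will be calculated for each group and 95% confidence intervals will be calculated".

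The other intervals in section 5.5 belong to the questionnaire scores ("along with confidence intervals for urinary symptom index, pain symptom index, etc"). No between-arm difference is specified for medication days or for medication amount.

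On supply, section 5.3 states: "Our pathway is to prescribe all patients with 10 tabs of Norco 5/325 1-2 tabs po q6H PRN". Patients who cannot take that product get an alternative narcotic on the same schedule. Patients without relief may receive further narcotics or Pyridium.

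**The concern.** The objective concerns how much medication patients take. The measure that is defined for each patient, and the only one that carries an interval, records whether they took any on a given day. On an as-needed schedule these are different quantities. Two arms could have the same proportion of use-days while patients in one arm take about twice as many tablets.

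The amounts table could show such a gap. With no per-patient summary, no between-arm difference and no interval, though, a reader could not judge whether the gap exceeds chance. The one medication result that does carry an interval could meanwhile suggest that the arms are alike. The hypothesis in section 1.1, that hyoscyamine patients "will not require additional pain medications (e.g. Pyridium, narcotics") relative to the tamsulosin arm, would then be judged on the less informative measure.

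**Working it through.** The plan gives no figure for this endpoint, so there is nothing to reproduce. The check has three steps.

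**1. What a use-day can contain.** From section 5.3, the schedule is 1 to 2 tablets every 6 hours as needed. The minimum on a use-day is 1 tablet. The ceiling is 2 × (24/6) = 8 tablets. Two use-days can therefore mean 2 to 10 tablets from the 10-tablet pack, a five-fold range at the same day count (2/7 = 0.286 of a week). The upper ends are dosing and supply ceilings, not expected use.

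**2. Size of a missed difference, with no supply limit.**

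Inputs from the documents: 47 patients per arm (section 5.4) and a diary running from stent placement to POD7, which is 8 days (section 5.6).

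Assumed inputs: each patient's daily chance of use follows Beta(2,2) in both arms (mean 0.5, variance 0.05). Tablets on a use-day are 1 + Poisson, with mean 4 in one arm and 2 in the other. Resupply is unlimited.

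Days:
- Expected difference: 0.5 - 0.5 = 0.
- Variance of a patient's proportion of days: 0.05 + (0.5 - 0.30)/8 = 0.075, where 0.30 = 0.5² + 0.05 is the mean squared chance of use.
- Standard error of the difference: √(2 × 0.075/47) = 0.0565.
- 95% interval: 0 ± 1.99 × 0.0565, or -11 to +11 percentage points.

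Amount:
- Expected difference: 0.5 × 4 - 0.5 × 2 = 1.0 tablet per day.
- Patient variance = 0.05 × m² + [0.5 × (s² + m²) - 0.30 × m²]/8, where m and s² are the mean and variance of tablets on a use-day.
- With m = 4, s² = 3: 0.80 + (9.5 - 4.8)/8 = 1.39.
- With m = 2, s² = 1: 0.20 + (2.5 - 1.2)/8 = 0.36.
- Standard error: √((1.39 + 0.36)/47) = 0.193.
- 95% interval: 1.0 ± 2.0 × 0.193, or 0.6 to 1.4.

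A simulation with tablets limited to 8 per day agrees. The days difference is 0.00 (-0.11 to 0.11), and its interval excludes zero in about 5% of runs. The amount difference is 0.99 (0.61 to 1.37 or 1.38), and its interval excludes zero in over 99% of runs.

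**3. Effect of supply.** Before any limit, about 69% of patients in the heavier-use arm and 31% in the lighter-use arm would need more than 10 tablets, so resupply matters. The table gives heavier minus lighter arm, with the average 95% interval.

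| Supply (assumed) | Days, points | Tablets per day |
|---|---|---|
| No limit | 0 (-11 to +11) | 1.0 (0.6 to 1.4) |
| One refill, 20 tablets in all | -5 (-15 to +5) | 0.7 (0.4 to 1.0) |
| Pack only, 10 tablets, nothing further | -14 (-21 to -6) | 0.2 (0.05 to 0.37) |
| Pack only, Pyridium on half of later symptomatic days | -7 (-16 to +2) | 0.2 (0.05 to 0.37) |
| Pack only, Pyridium on every symptomatic day | 0 (-11 to +11) | 0.2 (0.05 to 0.37) |

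A clear result in the wrong direction appears only in the third row, where patients who finish the pack take nothing more. Even there the amount difference depends on diary length. With a 15-day diary it nearly vanishes (0.05 tablets per day, -0.01 to 0.11), because both arms use up the pack.

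**The case against.** The strongest reply is that amount is already in the plan. The sentence before the day count commits to tabulating amounts, and for a goal declared mainly descriptive that table answers the objective, with use-days as a supplement. This stands in part. It would be wrong to infer that amount is neither collected nor reported. What is missing is a per-patient amount, a between-arm difference and an interval. Asking for them does not turn a descriptive goal into a hypothesis test: section 5.5 already attaches intervals to use-days, and the request is to give the same treatment to the quantity actually asked about.

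A second reply is that the illustration assumes what it shows. Equal use-days with a two-fold difference in tablets per day is an assumption, and more discomfort could well raise both together. That is right. The figures show how large the miss could be, not that it will happen. The interval on the day difference is also part of the illustration, since section 5.5 plans intervals per group only.

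A reader might go further and infer that use-days would favour the arm that took more tablets. The documents do not support that as an expectation. In this illustration a clear reversal needs patients who run out of the pack to take no refill and no Pyridium, and section 5.3 permits both further narcotics and Pyridium.

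A reader might also point out that section 5.5 does not say whether routine pack tablets count as additional medication. That is a real gap in definition: section 1.1 names narcotics as additional pain medication, while section 5.3 speaks of further narcotics after lack of relief. But it affects days and amount alike, so it is no argument that days are the wrong measure.

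**Conclusion.** The mismatch holds. The stated question is amount, and the only per-subject measure and the only medication-use interval are on days with any use. Amounts are tabulated, but with no specified means of judging a between-arm difference.

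That a use-day can mean 1 to 8 tablets follows directly from the dosing schedule. The numerical size (no difference in days alongside 1.0 tablet per day in amount) rests on assumed use rates, doses and resupply. With one refill the same pattern remains in weaker form. A reversal is a special case of exhausted supply with no substitute, and should not be presented as likely.

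This is a modest point and a cheap improvement. It concerns a secondary, mainly descriptive objective, and the primary non-inferiority conclusion does not depend on it.

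**What to change.** In section 5.5:

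- Make the main additional-medication summary each patient's amount per stented day from the diary. Count narcotic tablets by product, and Pyridium doses separately.
- State that tablets from the routine pathway pack count in the narcotic total.
- Report the between-arm difference with a 95% confidence interval, using a bootstrap or rank-based interval if amounts are skewed.
- Keep the kinds-and-amounts table and days with use as descriptive summaries.

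The cost is a few sentences of SAP wording and a little extra analysis. No new data field or extra patients are needed, because amounts are already to be tabulated from the diaries. An opioid-equivalence scale would have to be prespecified only if narcotic products were combined; counting by product avoids it.
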